#### 6.4.3 Clinical efficacy

Subjectively improvement will be measured using the Cleveland Clinic Constipation Score (CCCS) and Measure Yourself Medical Outcome Profile (MyMop) assessment pre- and post- intervention.

As part of NHS follow-up care, the patients will undergo repeat anorectal physiology studies (anorectal manometry) to assess the need for further treatment. The post-procedure findings will be compared with pre-procedure findings to identify any changes.

This information will be helpful to make an estimate of the sample size and follow-up rate for future studies.

### 7. Study population

Patients will be recruited from referrals to the pelvic floor multidisciplinary team (MDT) meeting and those who fulfil the inclusion criteria will be invited to participate in the study. The duration for participation is 12 months.

#### 7.1 Inclusion criteria

- Adult patients (age 18 80 years)
- Diagnosis of dyssynergic defaecation using ROME IV criteria.
  - The patient must satisfy diagnostic criteria for functional constipation and/or irritable bowel syndrome (IBS) with constipation
  - The IBS criteria includes recurrent abdominal pain, on average at least 1 day per week in the last 3 months, associated with 2 or more of the following: related to defaecation, associated with a change in

frequency of stools, or associated with a change in form (appearance) of stool.

- In IBS with predominant constipation (IBS-C) more than 25% of bowel movements are of Bristol stool form scale (BSFS) type 1 or 2 consistency, and less than 25% are of types 6 or 7.
- The functional constipation diagnostic criteria applies to those who do not meet the criteria for irritable bowel syndrome, whose stools are rarely loose without the use of laxatives, and must include 2 or more of the following: straining\*, lumpy or hard stools (BSFS 1-2)\*, sensation of incomplete evacuation\*, sensation of anorectal obstruction/blockage\*, manual manoeuvres to facilitate defaecation\*, fewer than 3 spontaneous bowel movements per week
- During repeated attempts to defaecate, there must be features of impaired evacuation, as demonstrated by 1 of the following 2 tests: abnormal balloon expulsion test or impaired rectal evacuation by imaging\*\*
- Inappropriate contraction of the pelvic floor as measured with anal surface EMG or manometry with adequate propulsive forces during attempted defaecation (as defined by age- and sex-appropriate normal values)
- Criteria fulfilled for the last 3 months with symptom onset at least 6 months before diagnosis.
- Ability to understand written and spoken English.
- Ability and willingness to give informed consent.
- \* More than 25% of defaecations.
- \*\* In our unit, imaging of rectal evacuation is performed using defaecography, and the assessment of pelvic floor contraction is assessed by evaluating the propulsive force, anorectal angle, and relaxation of the anal canal.

#### 7.2 Exclusion criteria

- Paediatric patients (age under 18 years)
- Diagnosis of defined structural or metabolic diseases that could cause constipation, such as Hirschsprung's disease, Parkinson's disease, multiple sclerosis, hypothyroidism (untreated), diabetic neuropathy, muscular dystrophy, motor neurone diseases, spinal injury leading to paraplegia, cauda equina syndrome
- Psychiatric or physical inability to comply with the study protocol (including e-diary assessments) at investigator discretion.
- Contra-indications to BTXA such as allergies, pregnancy (or intention to become pregnant during study period), breastfeeding, generalised disorders of muscle activity, myasthenia gravis
- Contra-indications to infracoccygeal injection at injection site such as infection or pressure sore, spina bifida, pilonidal disease, bleeding disorders (including therapeutic anticoagulation)
- Morbid obesity (BMI  $\geq$  40)
- Defunctioning loop or end stoma in situ
- External rectal prolapse

### 8. Study design

The overall design is of a single-centre, prospective, uncontrolled, open-label observational study. Patients diagnosed with dyssynergic defaecation, using Rome IV criteria, will be identified from weekly pelvic floor MDT and current waiting list for biofeedback therapy and invited to participate. BTXA injection is not offered as an alternative to biofeedback and does not preclude patients from receiving biofeedback therapy as per standard treatment as this is not a study of treatment efficacy.

All participants will undergo BTXA injection within 12 weeks of recruitment.

Data collection:

- Baseline data collection from patient's initial symptoms questionnaire and anorectal physiology report (pre-procedure).
- MYMOP questionnaire (pre-procedure and at final follow-up)
- Patient and physician procedural questionnaire to be completed at the end of the BTXA injection procedure (see Section 5.3 and 5.4).
- Cleveland clinic constipation score and St. Mark's incontinence score to be completed by the patient at each follow-up.
- Anorectal physiology report (post-procedure) for anorectal manometry results at first follow-up.
- Any adverse events reported by the patient will be recorded on an adverse event form (see Section 5.4).

Data analysis:

- Feasibility and efficacy outcomes will be extracted from the questionnaires and reports and recorded onto Research Electronic Data Capture (REDCap).
- Anonymised summary data will be exported to Excel and descriptive statistics (e.g. mean, confidence intervals of effect) used to present data for publication.

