#### 6.2 Secondary objective

- To assess safety of this technique
- To assess patient acceptability of this technique
- To derive pilot clinical efficacy data to inform future trials

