#### Visit 2: consent and baseline data

A second appointment will be arranged to obtain consent should the patient wish to participate in the study, which may be undertaken by an appropriately trained

member of the clinical or research team. Patient's original symptom questionnaire and anorectal physiology reports will be obtained to extract baseline data (CCCS, evacuation time and completeness, quality of expulsive force, opening of the anorectal angle, relaxation of the anal canal, as well as squeeze and push pressures). The patient will then complete CCCS, SMIS, and MyMop questionnaires.

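### The pilot change in CCCS and MYMOP has no score at the injection visit, no rule choosing between two CCCS baselines, and no listed record of biofeedback or repeat BTXA

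*Combined protocol and SAP*

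**What the plan says.** **Purpose.** Section 6.2 lists among the secondary objectives "To derive pilot clinical efficacy data to inform future trials". Section 6.4.3 measures this by CCCS and MYMOP before and after the intervention, plus repeat manometry, and adds: "This information will be helpful to make an estimate of the sample size and follow-up rate for future studies". Under data analysis, Section 8 plans "descriptive statistics (e.g. mean, confidence intervals of effect) used to present data for publication". Section 11.2 rules out hypothesis testing.

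**Baseline.** Section 8 takes baseline data from the initial symptoms questionnaire. Section 9, Visit 2, says the patient's "original symptom questionnaire and anorectal physiology reports will be obtained to extract baseline data", with CCCS among the extracted items, and continues: "The patient will then complete CCCS, SMIS, and MyMop questionnaires". The Section 9 visit table also lists CCCS at Visit 2. No section says which CCCS value anchors the change.

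**Injection visit.** Section 9 (Visit 3 and the visit table) lists only the patient and physician procedure questionnaires, completed after the procedure. The patient form in Section 6.4.2 has no bowel-symptom item.

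**Timing.** Section 8: "All participants will undergo BTXA injection within 12 weeks of recruitment".

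**Other treatment.** Section 8 says the injection "does not preclude patients from receiving biofeedback therapy as per standard treatment as this is not a study of treatment efficacy". Section 12 says the follow-up assessments inform the need for further treatment, which may be biofeedback or another BTXA injection.

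**The concern.** Allowing biofeedback is a deliberate and explained choice, and it is not contested here. The difficulty lies in what is recorded around it.

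The plan produces a before-and-after change, describes it as an effect with a confidence interval, and intends it as input to a future sample size. That change can contain two components that have nothing to do with the injection: movement between the baseline score and the day of injection, and movement after biofeedback or a second injection. With the listed data, someone using the published interval could not separate the first component, and could separate the second only by going back to clinical records. The choice between two CCCS baselines taken at different times would also be open after the data are seen.

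The prospect of co-treatment is realistic. Patients are identified partly from the biofeedback waiting list (Sections 8 and 9), and Section 5.1 reports biofeedback success of 33% to 80%.

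**Working it through.** There is no plan figure to reproduce. The sample of 10 is a convenience sample (Section 11.1), and the documents give no SD, effect size, alpha or power. The check is therefore of what is measured when, followed by the timing arithmetic.

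**1. Scores by time point** (Section 9, visit text and table)

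| Point | Week | CCCS | MYMOP | SMIS |
|---|---|---|---|---|
| Original questionnaire | not fixed | yes, extracted | not listed | not listed |
| Visit 2 | 5-6 | yes | yes | yes |
| Visit 3, injection | 18 | no | no | no |
| Visit 4 | 22-24 | yes | no | yes |
| Visit 5 | 30 | yes | no | yes |
| Visit 6 | 42 | yes | yes | yes |

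CCCS has two pre-injection values, so drift from the original questionnaire to Visit 2 can be seen. MYMOP and SMIS have one each. No score covers Visit 2 to injection.

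**2. Share of the interval that precedes injection**

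Let w be the wait from Visit 2 to injection and f the time from injection to follow-up. The share is w / (w + f).

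- f to Visit 4: 22 - 18 = 4 to 24 - 18 = 6 weeks
- f to Visit 5: 30 - 18 = 12 weeks
- f to Visit 6: 42 - 18 = 24 weeks

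If the 12-week limit runs from Visit 2, w is at most 12:

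- Visit 4: 12/16 = 75% to 12/18 = 67%
- Visit 5: 12/24 = 50%
- Visit 6: 12/36 = 33%. Only this last figure applies to MYMOP.

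The table alone would permit 18 - 5 = 13 weeks, but that exceeds the stated limit and is not used. If the limit instead ran from the table's week 0, w would be at most 12 - 6 = 6 to 12 - 5 = 7 weeks. The shares would then be at most 50-64% (6/12 to 7/11), 33-37% (6/18 to 7/19) and 20-23% (6/30 to 7/31). That reading keeps the table's Visit 2 week but not its injection week, so it serves only as a lower range.

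**3. Scores exposed to later treatment**

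The need for further treatment is assessed from the repeat physiology, which takes place at Visit 4. After it come 2 of the 3 follow-up CCCS scores (Visits 5 and 6) and the only follow-up MYMOP, 42 - 24 = 18 to 42 - 22 = 20 weeks later.

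**4. Search for a co-treatment item**

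The data collection list in Section 8, Visit 2, the visit table and the source-data table in Section 14.2 name neither biofeedback nor repeat BTXA. The one listed treatment field is treatment of an adverse event (Sections 6.4.1 and 16). Section 11.2 has no rule for scores obtained after co-treatment.

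**5. Illustration only, with assumed values**

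With n = 10 the 95% interval half-width is 2.262/√10 = 0.72 SD of the change. Suppose a later two-arm trial (two-sided 0.05, 80% power) is planned with n per arm = 2(1.960 + 0.842)²/d². A true effect of 0.5 SD needs 63 per arm. If an unrelated shift of 0.1, 0.25 or 0.5 SD were read as part of the effect, the planned number would be 44, 28 or 16. The documents do not say whether any such shift exists or how large it would be.

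**The case against.** The protocol says plainly that this is not an efficacy study, tests no hypothesis and has 10 uncontrolled patients. Attribution is limited whatever is recorded, and sampling error alone is large. Visit 2 is labelled as the baseline visit. Eligibility requires criteria met for the last 3 months and symptom onset at least 6 months before diagnosis, so large drift over 12 weeks cannot be assumed. The eCRF is not among the documents and may already hold co-treatment fields. Section 14.1 lists clinic letters as electronic source data, so treatment of 10 patients at one site can probably be traced. The Visit 4 score should normally precede any repeat BTXA, although biofeedback could come earlier. SMIS is a safety measure in Section 6.4.1, not an efficacy measure.

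Most of this stands, and it limits the point. It does not supply a baseline rule or a planned co-treatment item. Nor can a score missed on the injection day be recovered.

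A reader might infer more than the documents support:

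- **That two thirds to three quarters of the observed change predates the injection.** The shares are of elapsed time, and the documents give no drift rate.
- **That no earlier drift can be seen at all.** The two CCCS values can show it up to Visit 2.
- **That permitting biofeedback is itself an error.** Sections 8 and 12 give the reason for it.
- **That co-treatment information will be lost.** It may be recoverable from the clinical record.

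**Conclusion.** The point holds for the secondary pilot-efficacy objective only. Followed as written, the plan gives a CCCS and MYMOP change that can include up to 12 weeks before injection and any response to later biofeedback or repeat BTXA, with an unspecified choice between two CCCS baselines. The 12-week figure assumes that the limit runs from Visit 2; a different starting point shortens the wait but does not remove the gap. The size of any resulting distortion is unknown, because the documents give no drift rate and no usable rate of co-treatment. The primary feasibility endpoint does not depend on these scores and is unaffected. This is a change that should be made because it is cheap and partly irrecoverable if missed. It is not a defect that threatens the study.

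**What to change.** 1. Have the patient complete CCCS and MYMOP, plus SMIS as the safety baseline, at Visit 3 before the injection. Use these as the baseline for change, and report Visit 2 to Visit 3 separately as pre-injection change. At minimum, name the Visit 2 CCCS, not the original questionnaire, as baseline.
2. Record in the eCRF the dates of any biofeedback (before consent and up to 6 months after injection), the date of any repeat BTXA, and the date of the original questionnaire.
3. Flag scores obtained after either treatment in a per-patient listing, and report 'change from baseline' rather than 'effect'.

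Side note: Section 8 counts 12 weeks from recruitment, while the Section 9 table labels week 0 as recruitment and puts injection at week 18. The two must be reconciled.

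**Cost.** Three short questionnaires at an existing visit, a few dated fields, one listing and a wording change. The patient has a few more minutes of forms on the injection day. The table assigns Visit 3 to the radiologist, so someone must be named to collect the forms there. The minimum version (Visit 2 CCCS named as baseline, co-treatment dated) needs no new assessment but leaves change from Visit 2 to injection unseen. Patient care does not change. Even the full version does not allow attribution to the injection without a control.

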### 9. Study procedures

#### **Recruitment**

Patients diagnosed with dyssynergic defaecation, using Rome IV criteria, will be identified from the weekly pelvic floor MDT and current waiting list for biofeedback therapy. These patients will be screened against the inclusion and exclusion criteria. Patients will be continually recruited until 10 patients have undergone the procedure, including re-recruitment for drop-outs.

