#### 6.4.2 Treatment acceptability

Treatment acceptability will be measured objectively by the recruitment rate and subjectively using a patient acceptability questionnaire, which will be completed by the participant at the end of the procedure. The questionnaire measures patient's overall opinion of the procedure, level of

pain during treatment, satisfaction with the duration of the procedure, and willingness to undergo the procedure again.

Question/Statement	Scoring
1. The procedure was painful.	□ Strongly agree □ Agree □ Neutral □ Disagree □ Strongly disagree
2. The procedure was embarrassing.	□ Strongly agree □ Agree □ Neutral □ Disagree □ Strongly disagree
3. The procedure was comfortable	□ Strongly agree □ Agree □ Neutral □ Disagree □ Strongly disagree

 
The procedure duration was too long.
 
	Strongly agree  Agree  Neutral  Disagree  Strongly disagree
5. What score corresponds best with your opinion of the treatment procedure? (10 = acceptable, 0 = unacceptable)	0 1 2 3 4 5 6 7 8 9 10 Unacceptable Neutral Acceptable
6. Reason for your answer in question 5.	(Free text)
7. Would you be willing to undergo this procedure again?	□ Yes □ No

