#### Visit 4: first follow-up

The patient will attend first follow-up 4-6 weeks after the injection and complete the Cleveland Clinic constipation scoring (CCCS) as well as St. Mark's incontinence scoring (SMIS). They also undergo a repeat anorectal physiology tests.

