#### Visit 5: second follow-up

The patient will be given the option of telephone, face-to-face, or electronic follow-up at 3 months following the injection and will complete the CCCS and SMIS. They will also be asked if they have experienced any adverse events.

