#### Visit 6: final follow-up

This will take place at 6 months following the injection and will be similar to the second follow-up but the patient will also be asked to complete a MYMOP follow-up questionnaire, and to rank their level of satisfaction with the treatment using a satisfaction thermometer.

Visit	Study Stage	Data		Week	Carried out by	Setting
0	Recruitment	N/A		0	Research team	Pelvic Floor MDT
1	Initial discussion	N/A		1-4	Clinical/research team	Phone
2	Consent and baseline data	CCCS SMIS Anorectal physiology MYMOP		5-6	Clinical/research team	Outpatient clinic
3	BTXA injection	Patient questionnaire Physician questionnaire	ting	18	Radiologist	Outpatient Ultrasound
4	First follow-up	CCCS SMIS Anorectal physiology	ts reporting	22-24	Clinical/research team	GI physiology
5	Second follow-up	CCCS SMIS	events	30	Clinical/research team	Outpatient clinic/ phone/ online form
6	Final follow-up	CCCS SMIS MYMOP follow-up Satisfaction thermometer	Adverse	42	Clinical/research team	Outpatient clinic/ phone/ online form

Study intervention (at visit 3):

Botulinum toxin type A injection (BTXA) – The intervention is an injection of 200 units of Botulinum toxin type A in to the puborectalis muscle under ultrasound guidance.

- In the prone position, the puborectalis muscle will be identified below the coccyx using ultrasound.
- After skin preparation using 70% Isopropyl Alcohol Pad, up to 5ml of local anaesthetic (1% lidocaine) an electromyography (EMG) needle will be inserted and the puborectalis muscle stimulated using a current to confirm correct needle position. Figure 3 demonstrates an example EMG trace on a healthy volunteer at rest (a) and under voluntary contraction (b)
- 200 units of BTXA (Botox, Allergan, Ireland) prepared in 2 ml of saline solution and drawn up using a 2ml syringe.
- 1ml (100 units) of BTXA solution is injected through the EMG needle into the puborectalis muscle to each side of the midline, achieving a total of 200 units.
- The needle is withdrawn, and the procedure is complete.

At the end of the procedure, the patient and physician both complete post-procedure questionnaires.

[figure not shown]

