At any stage of the study, expected adverse events will be recorded on the patient's eCRF. If no adverse events have been self-reported this will be confirmed with the patient at the end of every follow-up appointment as part of the follow-up procedure. Serious or unexpected adverse events will be recorded and also reported according to research governance framework guidelines (see Section 14).

Patients can withdraw at any point in the study without the requirement to provide a reason. The data collected from the point of consent to the point of withdrawal will be kept for analysis of retention and follow-up rate, as well as incidents of adverse events depending on the stage at withdrawal. Such patients will return to routine care.

					-~~{	Lon				

Figure 3a. EMG of puborectalis demonstrating tonic activity at rest

Figure 3b. EMG of puborectalis demonstrating voluntary contraction

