#### 11.1Sample size

The sample size of 10 is a convenience sample (achievable in 12 months) and is not based on *a priori* calculations of statistical power. In the event of preprocedure patient withdrawal, further recruitment will take place to achieve a total of 10 patients.

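### Does the plan lose a patient who withdraws partway through the injection visit from its feasibility and acceptability results?

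*Combined protocol and SAP*

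**What the plan says.** Two places set the number of patients. Section 9 (Recruitment): "Patients will be continually recruited until 10 patients have undergone the procedure, including re-recruitment for drop-outs". Section 11.1: "In the event of preprocedure patient withdrawal, further recruitment will take place to achieve a total of 10 patients". Neither says whether having undergone the procedure means that it was started or that the injection was given.

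The withdrawal paragraph of Section 9 allows exit at any time: "Patients can withdraw at any point in the study without the requirement to provide a reason". On the data: "The data collected from the point of consent to the point of withdrawal will be kept for analysis of retention and follow-up rate"; it then adds adverse events, according to the stage reached.

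The Visit 3 intervention starts with imaging: "In the prone position, the puborectalis muscle will be identified below the coccyx using ultrasound". It ends when the needle is withdrawn.

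Section 6.3 measures feasibility by a physician form due after each procedure and by the rate at which the muscle is identified on ultrasound and EMG. Section 11.2 adds the proportion successfully injected after identification on both. Neither section names a denominator. The patient form in Section 6.4.2 is one "which will be completed by the participant at the end of the procedure".

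**The concern.** The patient in question agrees to take part, comes to Visit 3, has the scan started, and then withdraws from the study before injection, for instance because of pain. A technical failure in a patient who stays in the study is a different case: Sections 6.3, 9 and 11 together point to counting that patient.

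Under Section 9 the withdrawing patient looks like a drop-out to be replaced. Under Section 11.1 the patient does not look like a pre-procedure withdrawal, because the scan is the first step of the intervention. The listed uses of withdrawn patients' data do not include feasibility or acceptability. Someone following these sentences literally might replace the patient and report results for completers only.

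That would flatter the technique. Feasibility is the primary objective, and Section 12 describes the aim as finding out whether the technique is acceptable to patients and physician. A patient who asks to stop is evidence on both. With about 10 patients, one omission is visible in every reported proportion.

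**Working it through.** **The plan's own figure.** The sample size of 10 is described in Section 11.1 as a convenience sample with no power calculation. There is no formula to reproduce.

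**The replacement rules side by side.**

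| Meaning of *undergone* | Section 9, Recruitment | Section 11.1 | Result |
|---|---|---|---|
| Procedure started | Patient already counts towards the 10; no replacement | Not a pre-procedure withdrawal; no replacement | Agree |
| Injection given | Patient is a drop-out; replaced | Not a pre-procedure withdrawal; no replacement stated | Differ |

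A patient who withdraws before the scan starts is replaced under both sections on either meaning. The difference needs the procedure to begin at the scan for Section 11.1 but to mean a completed injection for Section 9.

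**The data-use sentence.** It says that the data will be kept and names some uses. It does not say that these are the only ones. Section 11.2 refers to patients without excepting those who withdrew.

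**Capture at Visit 3.** The physician form asks about identification by ultrasound and by EMG, patient comfort, successful completion on a five-point agreement scale, and limitations in free text. It can record a stopped attempt even when the patient gives no reason. Section 11.2 also promises a qualitative summary of technical difficulties. The timing of later visits from the injection does not matter here, since the feasibility data and the acceptability form are collected on the day.

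**Size if a patient were left out.** The number of stops is an assumption; the documents give none. Exact (Clopper-Pearson) 95% limits for x successes out of n are the 2.5% point of Beta(x, n−x+1) and the 97.5% point of Beta(x+1, n−x). When x = n the upper limit is 100% and the lower is 0.025^(1/n); for 10/10 that is 0.025^(1/10) = 69.2%. All other patients are taken as successful.

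| Stops | Replaced, omitted | Replaced, counted | Not replaced, counted |
|---|---|---|---|
| 1 | 10/10 = 100% (69.2 to 100) | 10/11 = 90.9% (58.7 to 99.8) | 9/10 = 90.0% (55.5 to 99.7) |
| 2 | 10/10 = 100% (69.2 to 100) | 10/12 = 83.3% (51.6 to 97.9) | 8/10 = 80.0% (44.4 to 97.5) |
| 3 | 10/10 = 100% (69.2 to 100) | 10/13 = 76.9% (46.2 to 95.0) | 7/10 = 70.0% (34.8 to 93.3) |

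For one stop, counting the replaced patient moves the estimate by 100 − 90.9 = 9.1 points. Replacing or not, once the patient is counted, moves it by 90.9 − 90.0 = 0.9 points. If two completers had also failed the endpoint, the comparison is 8/10 = 80.0% against 8/11 = 72.7%, a shift of 7.3 points. Counting therefore matters much more than replacement.

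**How likely is it?** With an assumed chance q that a patient withdraws during Visit 3, the chance of at least one before 10 complete is 1 − (1 − q)^10:

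- q = 2%: 1 − 0.98^10 = 18%
- q = 5%: 1 − 0.95^10 = 40%
- q = 10%: 1 − 0.90^10 = 65%

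These rates must refer to withdrawal from the study, not merely to asking for the needle to be stopped. If half of those who stop remain in the study, q halves and the chances become about 10%, 22% and 40%.

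**The case for a change.** The strongest case for a change is that nothing in the plan instructs the analyst to count this patient. Section 8 says that all participants will receive the injection, which makes *injected* a natural reading of *undergone*. Any omission would bias results in the technique's favour. The remedy is cheap: define the term, state that every started scan is in the denominator, and add feasibility and acceptability to the listed uses of the data.

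Part of this stands. The term is undefined, the denominator is unstated, and omitting such a patient would be wrong. But silence is not an instruction to omit. The numerator in Section 11.2 is already defined by success, so it is informative only if unsuccessful attempts are in the denominator; an analyst has every reason to include them. A patient who withdraws may also decline the acceptability form, and that answer would be missing however the plan was worded. The retention summary would still show that the patient left after consent, so the event would not vanish from the report.

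**Conclusion.** No change is needed. This is missing detail that analysts fill sensibly, and no stated rule forces a wrong result. The sections on replacement are not in firm contradiction; they part only on one of two readings of an undefined word.

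The effect is zero if nobody withdraws during Visit 3 or if every started attempt is counted. If one patient did and was left out, the proportion would be overstated by about 7 to 9 points. The exact intervals in the one-stop comparison are already about 31 points wide at their narrowest (10/10). The study is descriptive, with no hypothesis test and no progression threshold, so no decision turns on the shift.

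This rests on two assumptions: that such withdrawals are few (the documents give no rate), and that the report counts every patient in whom the procedure was begun. A reader of the published results can check the second by comparing the number who started Visit 3 with the number injected.
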